17.2. SECONDARY EFFICACY

The secondary efficacy analyses will be performed for the full analysis set (FAS).

17.2.1. KEY SECONDARY EFFICACY ENDPOINTS

The key secondary endpoints, which are included in the hierarchical analysis described in [Section 7.5](#), are:

- percent change from baseline to Week 24 in LDL-C

Statistical Analysis Plan

- percent change from baseline to Week 12 in non-HDL-C
- percent change from baseline to Week 12 in TC
- percent change from baseline to Week 12 in apoB
- percent change from baseline to Week 12 in hsCRP

Key secondary endpoints of LDL-C, non-HDL-C, TC, and apoB will be analyzed using the same ANCOVA model described in [17.1.2](#).

Similar to the primary endpoint, missing data will be imputed using multiple imputation method as described in [17.1.3](#).

For hsCRP, a non-parametric (Wilcoxon rank-sum test) analysis with Hodges-Lehmann estimates and confidence interval will be performed because based on historical knowledge, publication precedence (Brendan etc., 2006) and recent data available, hsCRP is known to be skewed by extreme values and have non-normal distribution.

Graphic presentations (mean+/-SE) or median (IQR) for efficacy parameters will be provided.

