Each ANCOVA will be performed using the FAS, with patients included in their randomized treatment group regardless of the treatment they actually received. Same imputation method described for the primary endpoint will be used for those secondary endpoints included in the step-down procedure, while only observed data analysis will be used for other secondary and tertiary endpoints. For each lipid parameter and analysis time point, the LSM and SE will be provided for both treatment groups, along with the placebo-corrected LSM, its 95% CI and associated p-value.

The ANCOVA assumption of normality will be assessed. If non-normality of the data is found at any time point for any parameter, either the data will be transformed so that it is normally distributed or a nonparametric test will be considered instead of the planned ANCOVA.

Percent change from baseline to Week 24 and to Week 52 LDL-C will be analyzed similarly with patients in the FAS who did not receive additional lipid-lowering therapy by that time point (by Week 24 for the Week 24 analysis; by Week 52 for the Week 52 analysis) included in the analyses. Only observed case data will be used (no imputation for missing data). Output from each time point will include the LSM and SE for each treatment group, as well as the placebo-correct LSM, 95% CI, and p-value.

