APPENDIX 1. SCHEDULE OF EVENTS (SUBJECT VISIT SCHEDULE)

	Screen	Run-in		Treatment						
Visit	S1 ^{1,2}	S2	S3	T1	T2	T3/phone	T4	T5	T6/phone	T7/EOS ³
Week	Wk -5	Wk -4	Wk -1	Wk 0	Wk 4	Wk 8	Wk 12	Wk 24	Wk 36	Wk 52
Procedure	Day -35±7	Day -28±3	Day -7±3	Day 1	Day 29±3	Day 57±3	Day 85±3	Day 168±7	Day 252±7	Day 365 ±7
Informed Consent	X									
Enrollment Criteria	X									
Demographics	X									
Medical History	X									
HeFH Status Determination	X									
Concomitant Medications	X	X	X	X	X	X	X	X	X	X
Adverse Event Recording		X	X	X	X	X	X	X	X	X
Physical Exam				X						X
Weight ⁴	X			X	X		X	X		X
Height/BMI	X									
12-Lead ECG ⁵				X						X
Vital Signs ⁶	X	X	X	X	X		X	X		X
Serology ⁷	X									
Serum Pregnancy and/or FSH ⁸	X									
Urine Pregnancy Test ⁸				X						
TSH	X									
Clinical Safety Labs ⁹	X			X	X		X	X		X
Basic Fasting Lipids ¹⁰	X		X	X	X		X	X		X
HbA _{1c}	X			X			X	X		X
apoB				X			X	X		X
hs-CRP				X			X	X		X
Diet and exercise counseling ¹¹	X	X	X	X	X	X	X	X	X	X
Plasma PK								X		X
Establish Patient Eligibility				X						
Randomization				X						
IWRS Contact	X	X		X			X	X		X ¹²
Single-Blind Drug Dispensing		X								
Double-blind Drug Dispensing ¹³				X			X	X		
Drug Return/Compliance			X	X	X		X	X		X
Schedule next visit	X	X	X	X	X	X	X	X	X	

NOTE: For patients who withdraw from IMP treatment, they will continue to have visits according to the protocol schedule. Safety assessments should include clinical safety and basic lipid laboratories (except for apoB and hs-CRP), adverse events, PE, vital signs, and ECGs. For patients who withdraw from IMP treatment, but refuse to come to the clinic for assessments, assessments will take place by phone. The telephone contacts will occur according the protocol schedule with information regarding current health status and to collect information on AEs (eg, recent procedures, hospitalizations, and if the patient has died, the cause of death).

- ¹ An optional visit between Visits S1 and S2 may be completed if patient fails to meet TG entry criterion. If this optional basic fasting (minimum of 10 hours) lipid value visit is completed, the repeat lipid value will be used to determine eligibility.

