APPENDIX 4. DETAILS OF MULTIPLE IMPUTATION METHOD

Missing Week 12 values will be imputed based on baseline values. The following table details the possible cohorts and which cohorts will be used for imputation. Missing Week 24 values will be imputed in the same way.

	Treatment	Week 12 Value	On Treatment at Week 12	Imputation Cohort(s)
1	Placebo	Missing	Yes	Cohort 5: Placebo patients with non-missing Week 12
2	BA	Missing	Yes	Cohorts 6 and 8 BA patients with non-missing Week 12
3	placebo	Missing	No	Cohort 5: Placebo patients with non-missing Week 12
4	BA	Missing	No	Cohorts 5 and 7 Placebo patients with non-missing Week 12 and not on treatment
5	placebo	Non-missing	Yes	
6	BA	Non-missing	Yes	
7	placebo	Non-missing	No	
8	BA	Non-missing	No	

Imputation code for Cohorts 1-3.

```
proc mi;
where cohort in(1,2,3,5,6,8);
class trt01pn strata;
monotone regression;
var trt01pn strata base aval;
run;
```

Imputation code for Cohort 4.

```
proc mi;
where cohort in(4,5,7);
class strata;
monotone regression;
var strata base aval;
run;
```

Statistical Analysis Plan

Two hundred imputed datasets will be created, with results from the analysis of each imputed dataset (ANCOVA) combined using Rubin's method.

[REDACTED]

[REDACTED]

[REDACTED]

[REDACTED]

Version Number:
Version Date:

0.5
14June2018

Statistical Analysis Plan

Adverse Event Terms per Protocol	Associated MedDRA Preferred Terms
	increased
Renal disorders	Creatinine renal clearance abnormal
Renal disorders	Creatinine renal clearance decreased
Renal disorders	Glomerular filtration rate abnormal
Renal disorders	Glomerular filtration rate decreased
Renal disorders	Oliguria
Renal disorders	Prerenal failure
Renal disorders	Renal failure
Renal disorders	Renal function test abnormal
Renal disorders	Renal impairment
Gout	Gout

[REDACTED]

[REDACTED]

[REDACTED]

[REDACTED]

Addendum to Statistical Analysis Plan

Title: A LONG-TERM, RANDOMIZED, DOUBLE-BLIND, PLACEBO-CONTROLLED, MULTICENTER STUDY TO EVALUATE THE EFFICACY OF BEMPEDOIC ACID (ETC-1002) IN PATIENTS WITH HYPERLIPIDEMIA AT HIGH CARDIOVASCULAR RISK NOT ADEQUATELY CONTROLLED BY THEIR LIPID-MODIFYING THERAPYE

Protocol: ETC-1002-047

Clinical Phase: 3

Product: ETC-1002

Date: Dec 17, 2018

Addendum to the Statistical Analysis Plan for Study 1002-047

Post-hoc Analyses

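### hs-CRP key secondary: Appendix 4's imputation has no transformation for an endpoint the SAP calls skewed, so some imputed values would be negative and a little power would be lost

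*SAP*

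**What the plan says.** - **Test.** SAP 7.5 places percent change in hs-CRP at Week 12 last in the step-down sequence, at two-sided 0.05. SAP 17.2.1 says "For hsCRP, a non-parametric (Wilcoxon rank-sum test) analysis with Hodges-Lehmann estimates and confidence interval will be performed". Its reason is that "hsCRP is known to be skewed by extreme values and have non-normal distribution". For the other key secondaries, "Key secondary endpoints of LDL-C, non-HDL-C, TC, and apoB will be analyzed using the same ANCOVA model described in" 17.1.2, that is, with baseline and the stratification factors.
- **Whether hs-CRP is imputed.** Protocol 12.6: "Same imputation method described for the primary endpoint will be used for those secondary endpoints included in the step-down procedure". hs-CRP is one of those endpoints. In SAP 17.2.1 the imputation sentence, "Similar to the primary endpoint, missing data will be imputed using multiple imputation method as described in" 17.1.3, stands after the ANCOVA endpoints and before the separate hs-CRP paragraph.
- **Imputation model.** Appendix 4 gives two monotone regressions. The one for off-treatment active patients is fitted to placebo patients, with the model line "var strata base aval". The other adds treatment. Neither shows a transformation or a lower bound.
- **Pooling.** Appendix 4 has "results from the analysis of each imputed dataset (ANCOVA) combined using" Rubin's method. No rule is given for a Wilcoxon statistic or a Hodges-Lehmann estimate.
- **Source of missing values.** For patients off study drug, the note to Protocol Appendix 1 asks for "clinical safety and basic lipid laboratories (except for apoB and hs-CRP"). Missing hs-CRP may therefore be more frequent than missing LDL-C, and mostly off treatment.

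**The concern.** The SAP drops the normality assumption for the hs-CRP test but keeps it for the model that fills in the missing hs-CRP values. With a right-skewed, strictly positive variable, a linear model with constant normal residuals produces some concentrations below zero (percent change below -100%) and others far too high for patients with a low baseline. At stake is some power for the hs-CRP claim, and a confirmatory analysis set that contains impossible values.

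**Working it through.** **1. The plan's own figure.** Power is stated for LDL-C only. The difference in standard errors is 15 / (15 × √(1/500 + 1/250)) = 1 / 0.07746 = 12.9, so power is essentially 100%, consistent with the stated figure of more than 95%. The documents give no SD, effect or missing rate for hs-CRP.

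**2. Inputs.** From the documents: 500 vs 250 patients, two-sided 0.05, and the two Appendix 4 models. Assumed: log-normal hs-CRP with log SD σ of 0.9-1.2 (wider range 0.7-1.3); log-scale correlation ρ of baseline and Week 12 of 0.5-0.8; 15-20% lower geometric mean on active drug; 5-10% missing completely at random, half or all of it off treatment; no stratum effect. The simulations used 20 imputations. They pooled the Mann-Whitney estimate by Rubin's rules, which is itself an assumption because the SAP states no rule.

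**3. Share of negative imputed values.** For median m, regressing raw Week 12 on raw baseline gives in large samples:
- slope b = (e^(ρσ²) − 1) / (e^(σ²) − 1)
- intercept a = m·e^(σ²/2)·(1 − b)
- residual SD s = m·e^(σ²/2)·√(e^(σ²) − 1)·√(1 − b²)

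At σ = 1.0 and ρ = 0.6: b = 0.822/1.718 = 0.478; a = 1.649m × 0.522 = 0.860m; s = 2.161m × 0.878 = 1.898m. At median baseline the prediction is 0.860m + 0.478m = 1.338m, and P(negative) = Φ(−1.338/1.898) = Φ(−0.705) = 24%. Averaged over the baseline distribution this is about 22%; simulation at this trial's size gives 20-21%. The median cancels, so the share depends only on σ and ρ. Simulated shares for ρ = 0.5-0.8:

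| log SD | negative share of imputed values |
|---|---|
| 0.7 | 7-10% |
| 0.8 | 11-14% |
| 0.9 | 15-18% |
| 1.0 | 19-22% |
| 1.1 | 23-24% |
| 1.2 | 25-27% |
| 1.3 | 28-30% |

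If the imputed variable were percent change instead, 6-26% of imputed values would still fall below -100%.

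**4. Share of patients.** 5% × 15% = 0.75% and 10% × 27% = 2.7%, so about 1-3%, or 6 to 20 of 750 patients.

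**5. Where the cost comes from.** No observed percent change can be as low as -100%, so negative imputed values simply take the lowest ranks. Setting them to zero left Wilcoxon power unchanged: 44.9% vs 44.9% at 10% missing and 54.0% vs 54.0% at 5% missing (15% reduction, all missing off treatment). The cost comes from the spread. Residual SD is 1.898m at every baseline: about 190 percentage points of change at median baseline, and 1.898/0.368 = 5.16, or 516 points, one log SD below it. Imputed ranks for low-baseline patients are then mostly noise.

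**6. Power of the Wilcoxon test** (about 800 trials per row, Monte Carlo SE 1-1.7 points):

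| log SD, ρ | reduction | missing | off treatment | raw scale | log scale | observed cases |
|---|---|---|---|---|---|---|
| 1.0, 0.6 | 20% | 5% | half | 85.0% | 86.5% | 87.6% |
| 1.0, 0.6 | 20% | 10% | half | 79.5% | 82.0% | 85.1% |
| 1.1, 0.6 | 20% | 10% | half | 68.5% | 74.6% | 76.8% |
| 0.9, 0.7 | 15% | 10% | half | 73.1% | 77.2% | 79.0% |
| 1.1, 0.6 | 20% | 10% | all | 66.0% | 70.8% | 77.6% |

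Over the assumed grid the log scale gains about 1 to 6 points. It gained nothing at a 25% reduction with 5% missing (97.8% raw, 97.5% log) or at 30% with 10% missing (100% both).

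**7. Type I error.** With no effect (log SD 1.1, ρ 0.6, 10% missing), rejection was 2.5% with raw imputation, 3.6% with log imputation and 4.4% for the Wilcoxon on complete data.

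**8. Baseline as a covariate.** In 2000 trials at log SD 1.0, ρ = 0.6, a 15% reduction and all missing off treatment, raw Wilcoxon / log Wilcoxon / log rank ANCOVA gave 55/57/66% at 5% missing and 48/53/59% at 10%. Over the grid, rank ANCOVA adds about 3 to 10 points to log-scale imputation.

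**The case against.** **hs-CRP may not be imputed at all.** The order of sentences in SAP 17.2.1 allows that reading, SAP 17.1.3 speaks of lipid values, and under Protocol 12.1 the SAP prevails where the two differ. The protocol sentence is explicit and nothing in the SAP contradicts it, so imputation is the better reading. The doubt is real, and the SAP should remove it.

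**Appendix 4 is a sketch.** A programmer might transform hs-CRP anyway. That is possible, but no text asks for it.

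**Most of the gap to the observed-case result is intended.** In the last table row, 77.6 − 70.8 = 6.8 points remain after the scale is corrected. That remainder reflects the placebo-based assumption for off-treatment patients and the imputation itself, not the scale.

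**Checks exist.** SAP 17.2.3.2 to 17.2.3.4 give three analyses of the key secondaries without imputation. hs-CRP is also drawn at the IMP-withdrawal visit (Protocol 10.2.10), and the Week 12 analysis window is Days 72-127, so some patients who stop drug would have a value. These limit the problem and would reveal it, but they do not change the planned main analysis.

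**The Wilcoxon is a legitimate choice.** A reader might infer that the test is wrong because it has no covariates. The documents do not support that: Protocol 12.6 allows a nonparametric test, the SAP gives its reason, and percent change already uses baseline. Omitting the covariate costs precision and causes no bias.

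**Conclusion.** The concern holds in a limited form. The imputation shown does not suit hs-CRP as the SAP itself describes it. About 15-27% of imputed values would be negative at a log SD of 0.9-1.2 (7-30% over 0.7-1.3), and the misfit costs about 1 to 6 points of power at 15-20% reductions with 5-10% missing. The 5%-missing difference is close to simulation noise, and the cost all but vanishes at reductions of 25% or more.

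A reader might infer that the negative values invalidate the hs-CRP test or raise its false-positive rate. Neither follows: their sign does not move the rank test, and rejection under the null was below 5%. No other endpoint is affected. The figures rest on assumed log-normal hs-CRP, missingness completely at random and an assumed pooling rule. The missing pooling rule alone is only a missing detail.

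**What to change.** - **Main change.** Within the same pattern mixture model, impute log Week 12 hs-CRP from log baseline and strata (with treatment where Appendix 4 has it), then back-transform before computing percent change. Negative values then cannot occur.
- **Same edit.** Confirm that hs-CRP is imputed, and name the rank quantity and variance pooled over the 200 datasets.
- **Optional.** A rank ANCOVA with baseline hs-CRP as covariate would add precision. Its p-value would no longer match the Hodges-Lehmann interval exactly, which a table footnote should state.

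The cost is some programming and SAP text, with no new data. These choices belonged in the SAP before unblinding. The addendum records that unblinding has taken place, so the planned Wilcoxon stays the confirmatory test and any result from these changes must be labelled supplementary.

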17.2.2. OTHER SECONDARY EFFICACY VARIABLES & DERIVATIONS

- change from baseline to Week 12 in LDL-C
- change from baseline to Week 24 in LDL-C

Other secondary endpoints will be analyzed using descriptive statistics by treatment group using observed data as well as on-treatment approach.

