6. Test the percent change from baseline to Week 12 in hs-CRP

In this hierarchical testing structure, each hypothesis is tested at a significance level of 0.05, two-sided. Statistical significance at each step is required in order to test the next hypothesis. If the primary endpoint meets the criteria for statistical significance, then the percent change from baseline to Week 24 in LDL-C will be tested; and so forth.

Percent change from baseline to Week 24 in LDL-C; absolute change from baseline to Weeks 12, 24,

and 52 in LDL-C; percent change from baseline to Weeks 12, 24, and 52 in HDL-C, non-HDL-C, TG, TC, apoB, and hs-CRP will each be analyzed using ANCOVA with treatment group, CV risk (ASCVD only; HeFH with or without ASCVD) and baseline statin intensity (high intensity, moderate intensity, low intensity) as factors and the relevant baseline as a covariate. Baseline for HDL-C, non-HDL-C, TG, and TC will be defined as the mean of the lipid values from Week -1 (Visit S3) and predose Day 1/Week 0 (Visit T1). If a repeat lipid measurement is performed at Week -1 (Visit S3), then baseline will be the mean of the lipid values from the second Week -1 assessment and predose Day 1/Week 0 (Visit T1). Baseline for apoB and hs-CRP will be defined as the predose Day 1/Week 0 (Visit T1) value. Each ANCOVA will be performed using the FAS, with patients included in their randomized treatment group regardless of the treatment they actually received. For each lipid parameter and analysis time point, the LSM and SE will be provided for both treatment groups, along with the placebo-corrected LSM, its 95% CI and associated p-value.

For all continuous efficacy endpoints (percent change from baseline in LDL-C, HDL-C, non-HDL-C, TC, TG, apoB, and hs-CRP; change from baseline in LDL-C; to Weeks 12, 24, and 52, as appropriate), the ANCOVA assumption of normality will be assessed. If non-normality of the data is found at any time point for any parameter, either the data will be transformed so that it is normally distributed or a nonparametric test will be used instead of the planned ANCOVA.

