5.2.2. Secondary Endpoints

1. Percent change from baseline to Week 24 in LDL-C
2. Percent change from baseline to Week 12 in non-HDL-C, TC, apoB, and hs-CRP
3. Absolute change from baseline to Weeks 12 and 24 in LDL-C

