12.6. Secondary and Tertiary Efficacy Endpoints

Key secondary efficacy endpoints are also of interest for this study, in terms of controlling the overall Type I error rate. A gatekeeping or stepdown approach will be used to test the primary efficacy endpoint and then specific secondary efficacy endpoints sequentially in order to preserve the study-wise Type I error rate. The sequence for the stepdown procedure in this study is as follows:

1. Test the primary efficacy endpoint: percent change from baseline to Week 12 in LDL-C
2. Test the percent change from baseline to Week 24 in LDL-C
3. Test the percent change from baseline to Week 12 in non-HDL-C
4. Test the percent change from baseline to Week 12 in TC
5. Test the percent change from baseline to Week 12 in apoB
6. Test the percent change from baseline to Week 12 in hs-CRP

In this hierarchical testing structure, each hypothesis is tested at a significance level of 0.05, two-sided. Statistical significance at each step is required in order to test the next hypothesis. If the primary endpoint meets the criteria for statistical significance, then the percent change from baseline to Week 24 in LDL-C will be tested; and so forth.

In general, change or percent change in lipid parameters at a given time point will be analyzed using similar ANCOVA model for the primary endpoint with treatment group, CV risk (ASCVD only; HeFH with or without ASCVD) and baseline statin intensity (high intensity, moderate intensity, low intensity) as factors and the relevant baseline as a covariate.

Baseline for HDL-C, non-HDL-C, TG, and TC will be defined as the mean of the lipid values from Week -1 (Visit S3) and predose Day 1/Week 0 (Visit T1). If a repeat lipid measurement is performed at Week -1 (Visit S3), then baseline will be the mean of the lipid values from the second Week -1 assessment and predose Day 1/Week 0 (Visit T1). Baseline for apoB and hs-CRP will be defined as the predose Day 1/Week 0 (Visit T1) value.

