17.3. TERTIARY EFFICACY

17.3.1. TERTIARY EFFICACY VARIABLES & DERIVATIONS

The tertiary efficacy endpoints are:

- Absolute change and percent change from baseline to Week 52 in LDL-C
- Percent change from baseline to Weeks 24 and 52 in non-HDL-C, TC, apoB, and hsCRP
- Percent change from baseline to Weeks 12, 24, and 52 in TG and HDL-C

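### The SAP plans only descriptive statistics for a declared secondary endpoint, absolute LDL-C change at Weeks 12 and 24, although the protocol specifies ANCOVA and the SAP keeps ANCOVA for the same variable at tertiary Week 52

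*SAP*

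**What the plan says.** Protocol 5.2.2 lists "Absolute change from baseline to Weeks 12 and 24 in LDL-C" among the secondary endpoints. The protocol then gives the method twice.

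- **Synopsis, Secondary and Tertiary Efficacy Endpoints.** One sentence opens with "Percent change from baseline to Week 24 in LDL-C; absolute change from baseline to Weeks 12, 24", carries on to Week 52 and to the other lipids, and closes with "TG, TC, apoB, and hs-CRP will each be analyzed using ANCOVA with treatment group, CV risk" and statin intensity as factors, and the relevant baseline as covariate.
- **Section 12.6.** It states as a general rule that "change or percent change in lipid parameters at a given time point will be analyzed using similar ANCOVA model for the primary endpoint". On output: "For each lipid parameter and analysis time point, the LSM and SE will be provided for both treatment groups, along with the placebo-corrected LSM", with its 95% CI and p-value. On missing data, the step-down endpoints are imputed, "while only observed data analysis will be used for other secondary and tertiary endpoints".

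SAP 17.2.2 lists change in LDL-C at Week 12 and at Week 24, and nothing else, as the other secondary variables. Its whole analysis plan for them is: "Other secondary endpoints will be analyzed using descriptive statistics by treatment group using observed data as well as on-treatment approach".

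SAP 17.3.1 lists "Absolute change and percent change from baseline to Week 52 in LDL-C" as tertiary, and SAP 17.3.3 sends the tertiary LDL-C endpoints to the ANCOVA of 17.1.2, each comparison at the 0.05 level. Protocol 12.1 gives the SAP precedence where the two documents differ.

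**The concern.** A secondary efficacy endpoint in a placebo-controlled trial is there to compare the arms. Under the operative SAP text, no between-arm estimate, interval or p-value in mg/dL is planned at Week 12 or Week 24. For the same variable, the lower-ranked time point gets a model and the two higher-ranked ones do not.

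The SAP does not explain this. Where it leaves ANCOVA for hsCRP (17.2.1), it states why: skewness and non-normality. Nothing similar is said here.

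Anyone who wants to report an absolute LDL-C difference at Week 12 or 24 must derive an unadjusted one from by-arm summaries or fit a model that the SAP does not contain. At stake are the SAP-level prespecification of that estimate and some precision, not the trial's main conclusions.

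**Working it through.** **1. Passages side by side**

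| Absolute LDL-C change | Status | Protocol method | SAP method |
|---|---|---|---|
| Week 12 | secondary | ANCOVA | descriptive, by arm |
| Week 24 | secondary | ANCOVA | descriptive, by arm |
| Week 52 | tertiary | ANCOVA | ANCOVA (17.1.2 model) |

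The protocol assigns ANCOVA at 3 time points and the SAP keeps it at 1, so 3 − 1 = 2 are dropped. Both are secondary.

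**2. Does the observed-data wording already imply descriptive statistics?** No. In protocol 12.6 that phrase is set against imputation, so it is a missing-data rule. The next sentence still asks for least squares means, the placebo-corrected difference, CI and p-value. The SAP reads it the same way at Week 52: 17.3.2 rules out imputation and 17.3.3 applies the ANCOVA.

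**3. Is it restored elsewhere?** SAP 17.1.2 already plans by-visit descriptive statistics for LDL-C change by arm, so 17.2.2 adds only an on-treatment version. The December 2018 addendum lists no analysis of absolute LDL-C change.

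**4. Sample size is no obstacle.** The plan's only power figure is for percent change (SAP 7.1): 500 and 250 patients, difference 15, SD 15, two-sided 0.05.

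- sqrt(1/500 + 1/250) = 0.0775, so SE = 15 × 0.0775 = 1.162.
- Difference / SE = 15 / 1.162 = 12.91, so power exceeds 0.999. This agrees with the stated figure of more than 95%.

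For absolute change the SD is not in the documents. With t(0.975, 748 df) = 1.963, the unadjusted half-width is 1.963 × 0.0775 × SD = 0.152 × SD. An assumed SD of 15 to 40 mg/dL gives about 2.3 to 6.1 mg/dL.

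**5. Precision given up without baseline adjustment.** Let r be the within-arm correlation between baseline LDL-C and its change. It is not in the documents and only its size matters. Assume r and SD are the same in both arms and that the strata add nothing further. Adjustment then multiplies the half-width by sqrt(1 − r²).

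| Assumed r | sqrt(1 − r²) | Unadjusted CI wider by | Patient equivalent 1/(1 − r²) |
|---|---|---|---|
| 0.1 | 0.995 | 0.5% | 1.01 |
| 0.3 | 0.954 | 4.8% | 1.10 |
| 0.5 | 0.866 | 15.5% | 1.33 |

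Under these assumptions the ratios do not depend on sample size.

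**6. If r differs by arm.** Take r = 0.5 on active, 0.1 on placebo and equal SDs. In units of SD², the unadjusted variance is 1/500 + 1/250 = 0.006.

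- *Separate slopes:* 0.75/500 + 0.99/250 = 0.00546, and sqrt(0.006/0.00546) = 1.048, so the unadjusted CI is 4.8% wider.
- *One common slope, as in 17.1.2:* the pooled standardised slope is about (500 × 0.5 + 250 × 0.1)/750 = 0.367. The residual variances are 1 − 2(0.367)(0.5) + 0.367² = 0.768 and 1 − 2(0.367)(0.1) + 0.367² = 1.061. Then 0.768/500 + 1.061/250 = 0.00578, and sqrt(0.006/0.00578) = 1.019, so the CI is about 2% wider.

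**The case against.** The strongest reply is that the change is permitted and costs little. Protocol 12.1 lets the SAP prevail, and section 12.6 phrases the ANCOVA as a general rule. The endpoint is outside the step-down sequence and has no power claim. Percent LDL-C change at the same visits keeps its ANCOVA with multiple imputation. The SAP's standard summaries (Appendix 1) include n, mean and SD, so a reader can form an unadjusted difference and CI. All of this stands as a limit on the weight of the point. It does not supply a reason for the change, and the synopsis names this endpoint and its weeks without the general qualifier.

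The upper precision figure can also be challenged. It needs r = 0.5 in both arms and a common SD, while SAP 17.1.2 itself expects unequal variances. This stands: step 6 of the working shows the loss can fall to about 2%, so 15.5% is the top of an assumed range and not an estimate.

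Two further reservations are fair. SAP 17.3.3 refers to tertiary LDL-C endpoints without spelling out absolute change, so the Week 52 contrast comes from reading it with 17.3.1, which does. The table templates mentioned in SAP section 8 are not among the documents, so the point concerns the SAP text and not the outputs actually produced.

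Finally, the addendum shows that the study has been unblinded and the planned analysis completed, so rewording the SAP can no longer restore its prespecification. The protocol text, however, remains a prior specification of model, covariates and output.

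**Conclusion.** The point holds. Without giving a reason, SAP 17.2.2 downgrades a declared secondary endpoint from the protocol's ANCOVA to by-arm description at both of its time points, and it is inconsistent with the SAP's own treatment of the same variable at Week 52.

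The consequence is limited. Error control and the primary and key secondary conclusions do not change. What is missing is a SAP-planned mg/dL difference adjusted for baseline LDL-C and the strata. The precision loss is modest: 0.5% to 15.5% in CI width for an assumed common r of 0.1 to 0.5, and about 2% in the unequal-r example with a common slope. The textual finding does not depend on these assumptions; only the precision figures do. It is worth correcting because the remedy is nearly free.

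**What to change.** Replace the analysis sentence in SAP 17.2.2 with:

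> Change from baseline to Weeks 12 and 24 in LDL-C will be analyzed with the ANCOVA model of 17.1.2 on observed data (FAS). LSM, SE, placebo-corrected LSM, 95% CI and a nominal p-value (outside the step-down sequence) will be reported. Descriptive statistics and on-treatment summaries are supportive.

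Since the addendum shows the study is already unblinded, the practical form is to run the two models (Weeks 12 and 24) and report them as the protocol 12.6 analysis, labelled as not planned in the SAP. If the sponsor prefers to keep the descriptive plan, the reason for departing from the protocol should be documented.

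Cost: no new data, and two extra runs of the existing 17.1.2 program. Before unblinding it would have been a wording change only. After unblinding, SAP-level prespecification cannot be recovered, but model, covariates and output are already fixed by the protocol.
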